staff versus testing only symptomatic students and staff. In this proposal, 12 middle and high schools from five predominantly African-American school districts in the St. Louis metropolitan area will be cluster randomized to screening testing plus symptomatic testing versus symptomatic testing alone. We will perform qualitative listening sessions and interviews with members of the school community including parents, teachers, administrators, and students to understand the facilitators and barriers to testing, the concerns regarding in-person school, and potential issues involving vaccine hesitancy evident in all populations and groups.

This study will provide critically needed, rigorous data to inform the utility of screening testing in schools and if it is important in aiding schools in the African-American community to return to in-person instruction. Additionally, the measurements of school-based transmission rates will help participating schools in the African-American community assess the impact of their mitigation strategies, demonstrate potential risk points for transmission that can be targeted for further intervention, and reassure the community on the safety of their schools. Finally, the study results will aid participating researchers, school districts and communities in understanding how to mitigate concerns about in-person schooling and the reliability of the mitigation strategies (with or without screening testing) in preventing COVID-19 transmission.

B Background

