The following five school districts in St. Louis County will be included: University City, Ferguson-Florissant, Normandy, Pattonville, and Jennings. Individuals who are students, staff, and household members of students and staff are eligible to participate in the various parts of the study. Sixteen middle and high schools from these school districts will participate. According to St. Louis County and regional hospital data, these districts are located in areas that have been most heavily impacted by COVID-19, especially in the early months of the pandemic. Additionally, all schools in this study receive Title 1 funding and have 100% of their students receiving free and reduced lunch. The percent of in-person attendance when available ranges from 20%-42%, and 18%-42% of families in these districts live below the poverty line.

D Study Procedures

D1 Testing Study Procedures

Recruitment and Consent

All research activities will occur among the students, parents/guardians, staff (teachers, aides, nurses, administrators) and household members of our participating school districts. All students (5-21 years old), school staff, and their household members (all ages) are eligible for inclusion in the study. Individuals will be excluded if they (or their parents/LAR) do not provide consent or are unable to provide saliva for testing.

Screening Testing Consent

Prior to starting screening testing, students, staff, and their household members will be consented or assented in-person (group or individual discussion), by phone, or by zoom. Middle and high school students under the age of 18 will provide assent (if cognitively able) for participation after we have obtained consent from their parent/LAR by phone, zoom or in person. Since household members/parents/LARs are not present in the school, they may receive a copy of the consent document prior to the consent discussion.

Symptomatic/Exposure Testing Consent

For symptomatic and/or exposure testing, we will obtain verbal consent and assent (when appropriate) prior to testing. A copy of the consent information will be provided. We will also have individuals sign an email communication form and note their email preferences. The email communication form might be in person or electronic since parents/LARs are not present at the school.

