The questions in both of these include those related to: housing, employment, health insurance, languages spoken in the home, family income, work PPE and distancing, vaccinations, reasons for getting/not getting a COVID-19 vaccine, alcohol and tobacco/nicotine use, previous COVID-19 testing, accessibility to testing, perceived accuracy of testing, perceived benefits of testing, perceived risks of testing, intention to be testing, food insecurity, trust of sources to provide correct information about COVID-19, height, weight, health status, teacher or student, grade taught/ grade student is in, type of learning, classroom setting, sports/ band/choir/drama/clubs participation, before or after school program, percent of time spent closer than 6 feet to others, percent of time mask is worn, percent of time able to social distance, access to handwashing, COVID symptoms, quarantine status/length, COVID test results, type of test, last day in person school, mitigation strategies by the individual/case at school, exposures outside school setting in the 14 days prior to exposure (contact) or 2 days prior to symptom onset (COVID sample if asymptomatic) (case) up until isolation, mask/social distance used at outside school settings. To reduce the length of the interview, these individuals will also be asked to complete some questions via RedCap.

Screening Testing: Schools will be randomized to perform or not perform weekly saliva-based screening testing for students and staff in addition to symptomatic testing. Eight of the sixteen schools will be randomized to screening testing.

Students, staff, and household members attending in-person school will be offered weekly screening testing if they (or their household member) are attending a school randomized to this strategy. Prior to the start of screening testing, participants will provide informed consent/assent and demographic information. The saliva-based testing method will allow for staff and students to obtain the sample at home or school, then give it to school personnel; study team members will label and transport the specimens for testing to the WUSTL laboratory. Weekly screening testing will be available whenever in-person school is provided for schools randomized to this strategy, including during summer sessions.

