Power calculation: A cluster randomized trial (CRT) will be conducted at 12 schools that provide symptomatic SARS-CoV-2 testing to students and staff. Schools will be randomized 1:1 to either screening testing plus symptomatic testing, or symptomatic testing only. All participants including students and staff will receive the same assignment within a given school. The primary outcome is transmission rate, defined as the ratio of the number of contacts testing positive for SARS-CoV-2 to total number of contacts for each school-based case. We hypothesize that schools performing screening testing will have lower transmission rates than routine symptomatic testing. We expect that transmission rates with screening testing or routine symptomatic testing will be 2% and 8%, respectively. With the assumptions that the intracluster correlation coefficient (ICC) is 0.02 and the standard deviation of transmission rate is 0.22, 6 schools in each arm with an average of 117 participants per school will achieve 80% power to detect a difference in transmission rates between the two study arms using a two-sided t-test at a significance level of 0.05 (Table 3). PASS 15.0 was used to conduct this power analysis.

Table 3. Sample Size

| ICC | Standard deviation | # of participant per school |
|------|--------------------|-----------------------------|
| 0.01 | 0.25 | 83 |
| | 0.30 | 188 |
| | 0.33 | 376 |
| | 0.35 | 803 |
| 0.02 | 0.22 | 117 |
| | 0.23 | 164 |
| | 0.24 | 252 |
| | 0.25 | 486 |
| 0.03 | 0.20 | 221 |
| | 0.21 | 806 |

Analysis plan: The generalized estimating equation (GEE) model with appropriate link function (e.g., identity for primary outcome) will be used to analyze the CRT data, in which the correlation among participants within each school needs to be considered. The autoregressive of first order as a working correlation structure will be used, and participants with missing values will be excluded from the GEE analysis. The GEE model includes the group indicator and other potential factors, including: race/ethnicity, insurance status, age, gender, underlying diagnoses, masking, distancing, ventilation, location of transmission. Least square means for the primary outcome per group will be estimated, and the standard errors will be calculated with the GEE sandwich method when accounting for within-school correlation. All analyses will be conducted using SAS (SAS Institute, Cary, NC) at the two-sided significance level of 0.05.

Data Management.

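### The primary GEE analysis uses sandwich standard errors for 12 (or 16) schools with no small-sample correction or school-based degrees of freedom; as a Wald z test its size is about 0.10 (or 0.09), not 0.05

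*Combined protocol and SAP*

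**What the plan says.** The analysis plan in Section E is one paragraph. It specifies a GEE model with identity link for the primary outcome, the group indicator and a list of other factors. On correlation it says "The autoregressive of first order as a working correlation structure will be used". For precision it specifies that "the standard errors will be calculated with the GEE sandwich method when accounting for within-school correlation". These accompany the group estimates, on which the plan says "Least square means for the primary outcome per group will be estimated". Everything is to be run in SAS "at the two-sided significance level of 0.05". Nothing in the document names a small-sample correction to the sandwich variance, a test statistic (Wald or score), a reference distribution (z or t) or degrees of freedom.

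The power paragraph of Section E refers to a two-sided t-test without giving its degrees of freedom, and states that "6 schools in each arm with an average of 117 participants per school will achieve 80% power".

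The number of schools is not consistent. Section A has "12 middle and high schools from five predominantly African-American school districts", and Section E also uses 12. Section C (Study Setting and Populations) says "Sixteen middle and high schools from these school districts will participate", and Section D1 (Screening Testing) says "Eight of the sixteen schools will be randomized to screening testing".

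**The concern.** The sandwich variance is consistent as the number of clusters grows. Participants do not count towards that, because everyone in a school has the same assignment. With 6 or 8 schools per arm there are two separate errors. The uncorrected sandwich is biased downwards, because it divides by the number of schools rather than by that number minus the parameters estimated from them. In addition, a z critical value ignores the uncertainty of a variance estimated from only 10 or 14 degrees of freedom. Both make the test reject too often and the interval too short.

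Least square means with sandwich standard errors are Wald quantities, so the natural reading of the plan is a Wald test and Wald intervals. On that reading, the trial's only primary comparison would be declared positive under no effect about twice as often as stated with 12 schools. The power statement would not reveal this if it also fails to count schools.

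**Working it through.** **Inputs.** All are from Section E unless noted: two-sided alpha 0.05; rates 2% and 8% (difference 0.06); SD 0.22; ICC 0.02; 6 schools per arm, 117 participants per school. The alternative of 16 schools, 8 per arm, is from Sections C and D1. K is the total number of schools and m the number per school.

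**1. Reproducing the stated power.** SE = sqrt[2 × SD² × (1 + (m − 1) × ICC) / ((K/2) × m)].

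For K = 12: sqrt[2 × 0.0484 × 3.32 / 702] = 0.0214, and 0.06 / 0.0214 = 2.80. For K = 16 the divisor is 936, which gives SE 0.0185.

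| Reference, K = 12, m = 117 | Power |
|---|---|
| Normal | 80.1% |
| t on 1402 df (participants: 12 × 117 − 2) | 80.0% |
| t on 10 df (schools: 12 − 2) | 71.5% |

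The stated 80% at 117 per school is therefore reproduced, but not with school-based df. The same formula on all ten rows of Table 3 gives 80.0–80.2% (normal), 79.97–80.08% (participant df) and 71.4–71.6% (t on 10 df). So the t-test named in the power paragraph does not supply school-based df.

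On 10 df, 80% power in the headline row needs 320 per school. With K = 16 and t on 14 df, power at 117 per school is 85.3%, and 77 per school is enough for 80%.

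**2. Size of the uncorrected sandwich test.** With equal school sizes and only the group term, the sandwich variance equals (K − 2)/K times the unbiased between-school variance. A Wald z test then rejects when the ordinary school-level t statistic exceeds 1.96 × sqrt[(K − 2)/K].

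| | K = 12 | K = 16 |
|---|---|---|
| Effective threshold on the t scale | 1.789 | 1.833 |
| Correct threshold, t on K − 2 df | 2.228 | 2.145 |
| Size, sandwich with z | 0.104 | 0.088 |
| Coverage of nominal 95% interval | 89.6% | 91.2% |
| Size, sandwich with t on K − 2 df, variance uncorrected | 0.069 | 0.065 |
| Size, corrected variance with t on K − 2 df | 0.050 | 0.050 |

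The fifth row shows that changing only the reference distribution is not enough.

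**3. Interval width.** The ratio to the proper width is 1.789/2.228 = 0.80 (K = 12) and 1.833/2.145 = 0.85 (K = 16). On the plan's inputs the half-width is 1.789 × 0.0214 = 3.8 points instead of 2.228 × 0.0214 = 4.8 (K = 12), and 3.4 instead of 4.0 (K = 16). The hypothesized difference is 6 points.

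**4. Simulation checks.** A simulated AR(1) GEE with normal outcomes and 117 per school (4,000 runs) gave Wald z sizes of 0.102 and 0.089. A beta-binomial simulation at equal school sizes with true rates of 2–8% (20,000 runs per setting) gave 0.092–0.104 with 12 schools and 0.079–0.089 with 16. In that simulation the Kauermann-Carroll correction with t on K − 2 df gave 0.039–0.050 and 0.040–0.049.

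**5. Sensitivity to inputs the documents do not give.** With an assumed coefficient of variation of school size of 0.6 and size-proportional weights, Wald z size was 0.12–0.14 (12 schools) and 0.10–0.11 (16). With assumed school-level covariates it was 0.13 and 0.10 for one covariate, and 0.20 and 0.15 for three. These show direction only; the verdict does not rest on them.

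**The case against.** The strongest reply is that the plan names a standard error and an alpha level but no test. A generalised score test would fit the text and hold its size. With equal schools it rejects when t² > 3.84 × (K − 2)/(K − 3.84), which gives 0.055 with 12 schools and 0.054 with 16; simulated values were 0.042–0.055. That is correct, so the inflation is conditional on a Wald z reading. It does not clear the plan. The error rate then depends on a choice left open, and a score test would not repair the sandwich standard errors and intervals that are to be reported.

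Second, with 16 schools power is 85.3%, above the stated 80%. This stands: the power shortfall exists only if 12 is the operative number. Size of 0.088 and the short interval remain at 16.

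Third, neither simulation uses the plan's exact outcome, a per-case attack rate averaged within school, and the closed form assumes equal schools with roughly normal means. The third decimal should not be relied on. Sizes of about 0.10 and 0.09 are adequately supported.

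Fourth, AR(1) does not cause the size problem. Agreed; it is a secondary matter of efficiency.

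**Conclusion.** The concern holds. As written, the primary analysis pairs an uncorrected sandwich variance with 12 or 16 randomized units and gives no small-sample reference. Under a Wald z test the size is about 0.10 with 12 schools or 0.09 with 16, and intervals are 80% or 85% of their proper width. These figures assume equal school sizes, only the group term, and approximately normal school means.

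The power finding does not depend on the Wald reading. Table 3 was computed without school-based df, and a t reference on 10 df lowers the headline 80% to 71.5% for 12 schools. The point must be fixed because it governs the error rate of the primary comparison.

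**What to change.** In Section E, name the primary test and its reference distribution:

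- Use a bias-corrected sandwich variance (for example Kauermann-Carroll or Fay-Graubard) with a t reference on the number of schools minus the number of school-level parameters. If school sizes vary widely, prefer Mancl-DeRouen: at the assumed coefficient of variation of 0.6, Kauermann-Carroll with t ran at 0.053–0.070 and Mancl-DeRouen with t at 0.032–0.045.
- Alternatively, use a t-test on school-level rates, which gave 0.040–0.050 in the same setting.
- Reconcile 12 and 16 schools, and recompute Table 3 with the same df for the actual number.
- State whether masking, distancing and ventilation enter at school or person level. Section D1 collects masking and distancing at both levels, and school-level terms use up df.
- Secondary: state the within-school ordering that AR(1) needs, or use an exchangeable structure, which matches the single ICC in the power calculation.

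The cost is plan wording and a recomputed table, with no new data. The interval widens, and stated power at 117 per school becomes 71.5% (12 schools) or 85.3% (16). Because this version is dated May 2023 and Section F has the trial statistician in quarterly data reviews, the change should be dated, with a record of whether it was made without knowledge of results by arm.
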